6.3.1 Patient characteristics and discontinuation

The number of patients in each population will be presented. The number of patients discontinued and reasons for discontinuation during the lead-in period and during the randomised treatment period will be presented. Demographic data and other baseline characteristics will be presented for all randomised patients by randomised treatment/dose.

6.4 Method of statistical analysis

6.4.1 Efficacy

6.4.1.1 Triglycerides levels

The following analyses will be performed for TG:

- Last observation carried forward (LOCF) on the ITT (Intention to treat) population for primary and secondary endpoints at week 8. This will be the primary analysis.
- Observed data on the per Protocol (PP) population for primary and secondary endpoints at week 8.

Initially a Friedman analysis will be performed, then, for comparing each one of Rosuvastatin groups against placebo group at week 8 a U Man Whitney test will be done. Also, the percentage of reduction –week 8 minus basal- obtained in the placebo group will be contrasted against the percentage of reduction in each one of the Rosuvastatin groups using a U Man Whitney test. In all the cases a p < 0.05 will be considered significant.

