3.5 Method of assigning patients to treatment groups

The actual treatment assigned to individual patients will be determined according to a non-centre specific randomisation scheme, which will be produced by AstraZeneca using an AstraZeneca computer software tool, prior to the inclusion of the first patient.

Once a patient has signed the written informed consent form, they will be allocated an enrolment code (e-code) that is a unique identifying number that must be used as the identification number throughout the study. If a patient discontinues from the study, the e-code will not be re-used.

Patients who failed to qualify for the study based on inclusion/exclusion criteria and were not randomised will **not** be allowed to re-enter the study.

The study doctor will establish patient eligibility before treatment randomisation. At Visit 2.1 (Week 0) patients who satisfy the entry criteria will be randomly assigned to receive either rosuvastatin 10 mg, rosuvastatin 20 mg or placebo with a 1:1:1 randomisation ratio. IVRS must be used to randomise the patient. It is important that patients are not randomised ahead of their randomisation visit (Visit 2.1).

At visit 2.1 it is important to check that the medication identification number matches the number allocated by IVRS, prior to treatment dispensation. If a treatment is incorrectly dispensed (i.e., medication identification number does not match the number allocated by IVRS), the error should be rectified and AstraZeneca should be notified as soon as the error is discovered.

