4. MEASUREMENTS OF STUDY VARIABLES

4.1 **Primary variable**

The primary variable is the change TG from baseline to week 8.

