6.2 Description of outcome variables in relation to objectives and hypotheses

Each outcome variable relates to the corresponding objective as described in Section 4.7.

Primary efficacy outcome variable

1. Percentage change in TG levels from baseline to week 8.

Secondary efficacy outcome variables

- 1. Percentage change in non-HDL-C levels from baseline to week 8.
- 2. Percentage change in lipids and lipoproteins (different to TG and non-HDL-C) from baseline to week 8 (LDL-C, TC, HDL-C, ApoA1, ApoB, TC/HDL-C; LDL-C/HDL-C; nonHDL-C/HDL-C and ApoB/ApoA1 indexes).
- 3. Percent change of hsCRP from baseline to week 8.

Secondary safety outcome variables

1. Safety evaluation as determined by the incidence and severity of adverse events and abnormal laboratory values

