6.3 Description of analysis sets

Efficacy

Efficacy data will be evaluated based on the intention-to-treat (ITT) and per-protocol (PP) populations.

The ITT population will consist of randomised patients who have a baseline reading and at least one post-baseline reading for at least one efficacy variable, and who have taken at least one dose of study medication. The PP population will consist of all patients in the ITT population who did not have a major protocol violation or deviations that would be likely to affect the efficacy outcomes (i.e. patients taking lipid lowering therapy other tan study drugs).

Patients will be evaluated using randomised treatment/dose (i.e., rosuvastatin 10 mg, rosuvastatin 20 mg, or placebo) for the ITT efficacy analyses, and actual treatment/dose received for the PP efficacy analyses.

For the test of superiority (versus baseline), the ITT population is the primary analysis population. Analyses of the ITT population will be performed using the last observation carried forward (LOCF) method and also using observed data. The LOCF analysis is the primary analysis. LOCF is defined as the last non-missing post-baseline value for a variable carried forward. If no non-missing value exists after baseline, the value will be treated as missing in the analysis. The analyses will be repeated for the PP population as a robustness check using only observed data. Any differences in interpretation of the results from the ITT population will be explored. For tests of no clinically significant deterioration from baseline the ITT and PP populations will be considered equally important.

Safety

The randomised safety population will consist of all patients who were randomised and took at least 1 dose of study medication. Safety data will be evaluated using actual treatment/dose received. In addition safety data from the lead-in period will be evaluated for all patients who enter the lead-in period.

The safety, ITT, and PP populations (including violations and deviations) will be determined prior to treatment unblinding.

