6.5 Determination of sample size

The primary outcome variable for this study, which the sample size calculation has been based on, is the change in TG levels from baseline to Week 8.

Hypothesis testing will be undertaken to assess whether this change from baseline in TG levels is significantly different from zero (i.e., testing for a positive effect compared to baseline) for each of the rosuvastatin 10 mg and rosuvastatin 20 mg treatment groups. Similar hypothesis testing will also be performed for the placebo group.

No adjustment will be applied for the two rosuvastatin groups since the hypothesis testing in each of the treatment groups is independent. Therefore a 2-sided significance level of 5% will be applied for testing for a positive effect versus baseline. The required power is 90%.

Data taken from the literature suggest that an intervention with RSV will reduce TG levels between 22 and 25% average, with a maximum of 37% from baseline (expected p for sample 1(placebo):0.029; expected p for sample 2(RSV):0.229). We need a minimum of 67 fully evaluable patients per treatment arm to reach the 2-sided alpha 0.050 with a potency of 90% and a confident interval of 95%. Increasing sample size to 100 per arm increases potency to 97%.

As there are about 10 to15% patients that would probably not complete the 8 weeks treatment period (non-evaluable patients), we will increase the patients per treatment arm to 110 (a total of 330 randomised patients). As we have the facility of doing the trial in at least 10 centers, we can easily reach the target patients per treatment arm. Assuming a screen failure rate of 3:1 we will require approximately 990 patients to enter the study.

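### Each rosuvastatin dose is compared with placebo by two unranked, unadjusted Mann-Whitney tests; adjusting for baseline triglycerides would gain some precision at no cost

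*Protocol*

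**What the plan says.** After an initial Friedman analysis, Protocol 6.4.1.1 lists two between-arm tests for TG, and the synopsis repeats them.

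- The first uses the week-8 level: for "comparing each one of Rosuvastatin groups against placebo group at week 8 a U Man Whitney test will be done".
- The second uses percentage reduction: the value "in the placebo group will be contrasted against the percentage of reduction in each one of the Rosuvastatin groups using a U Man Whitney test".

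Neither has a covariate, neither is named as the deciding test, and both use p < 0.05. Section 6.4.1.2 extends the approach to the other lipids, the apolipoproteins and CRP.

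Sections 4.7 (Table 5) and 6.2 give the primary outcome variable as "Percentage change in TG levels from baseline to week 8". Section 4.1 does not mention a percentage: "The primary variable is the change TG from baseline to week 8".

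Baseline TG is available. Visit 2 TG is an inclusion criterion (Section 3.3.2, 200 to below 800 mg/dL), and Section 6.3 requires a baseline reading for entry to the ITT set.

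**The concern.** Entry TG may span a four-fold range, so baseline should explain a good part of the variation in week-8 TG. The level test leaves that variation in the error. The percentage-change test removes some of it but over-corrects. Ranking percentage change is the same as ranking log(week 8) minus log(baseline), which fixes the baseline slope at 1. Within-patient variation puts the true slope below 1, and selecting patients on TG at two visits lowers it further.

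At stake are power and the width of the interval for each dose against placebo, for TG and for the secondary variables. A second cost is that two unranked tests of one question can give different answers.

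**Working it through.** **The plan's own sample size.** Section 6.5 uses 0.029 against 0.229, two-sided 5% and 90% power, and states 67 per arm. With mean proportion 0.129:

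- n = [1.960·√(2·0.129·0.871) + 1.282·√(0.029·0.971 + 0.229·0.771)]² / 0.200² = (0.929 + 0.580)² / 0.04 = 56.9
- with continuity correction: (56.9/4)·[1 + √(1 + 4/(56.9·0.200))]² = 66.6, so 67

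The figure reproduces. The formula contains no SD and no baseline to week-8 correlation, so the protocol cannot itself show what adjustment is worth.

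**Inputs for the comparison.**

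- Evaluable patients: 285 to 300 in three arms (Section 3.1). The lower end is 285/3 = 95 per arm.
- Planned effect: read as mean reductions, (1 − 0.229)/(1 − 0.029) = 0.794, about 20% below placebo. I also used 15% as a smaller effect.
- Assumed, not in the protocol: log-normal TG, population median 180 mg/dL, between-patient log SD 0.45, within-patient log SD 0.25 to 0.35, selection to 200 to below 800 mg/dL at Visits 1 and 2.

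**Ordering.** The residual variance of log week-8 TG minus b times log baseline is smallest when b is the true slope. The level test uses b = 0 and the change score uses b = 1. ANCOVA estimates b, so it does better than both whenever the slope lies strictly between 0 and 1.

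**Slope and variance under these assumptions.** Without selection the slope is 0.45²/(0.45² + within SD²), which is 0.76, 0.69 and 0.62 for within SD 0.25, 0.30 and 0.35. After selection at both visits:

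| Within SD | Correlation | Slope | ANCOVA variance / level | ANCOVA variance / log change |
|---|---|---|---|---|
| 0.25 | 0.50 | 0.64 | 0.75 | 0.91 |
| 0.30 | 0.42 | 0.57 | 0.83 | 0.89 |
| 0.35 | 0.34 | 0.50 | 0.88 | 0.88 |

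Against log change, 95 patients with ANCOVA are worth about 95/0.91 = 104 to 95/0.88 = 108 without it. The textbook equal-variance ratio (1 − ρ²)/[2(1 − ρ)] gives 0.75 at ρ = 0.5, which overstates the gain here because selection makes the baseline SD smaller than the week-8 SD.

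**Simulated power (%), 3,000 trials per cell, 95 per arm.** MW is Mann-Whitney.

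| Within SD | True reduction | MW level | MW % change | Log ANCOVA | Gain over % change |
|---|---|---|---|---|---|
| 0.25 | 15% | 84.7 | 89.9 | 93.5 | 3.6 |
| 0.30 | 15% | 76.0 | 78.7 | 85.0 | 6.3 |
| 0.35 | 15% | 66.8 | 66.0 | 73.4 | 7.4 |
| 0.25 | 20% | 98.2 | 99.5 | 99.8 | 0.3 |
| 0.30 | 20% | 95.8 | 96.6 | 98.6 | 2.0 |
| 0.35 | 20% | 90.4 | 90.5 | 94.4 | 3.9 |

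With no true effect, every method rejected in 4.2 to 5.3% of trials. The two planned tests disagreed on significance in 15 to 21% of trials at a 15% reduction and in 2 to 9% at 20%.

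**A wider range.** A second model had median 300, log SD 0.5, baseline truncated to 200 to 800 mg/dL and 1,000 trials per cell. At a 20% reduction, power for level / % change / log ANCOVA / rank ANCOVA on % change was:

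- ρ 0.4 before truncation: 87 / 84 / 92 / 90
- ρ 0.6: 91 / 95 / 98 / 97
- ρ 0.8: 95 / 100 / 100 / 100

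The first line is the worst case found: a gain of about 8 points over % change.

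**The case against.** The strongest reply is that the relevant planned test already uses baseline and has ample power. Percentage change is the named primary variable. At the planned difference of about 20%, most settings give that test over 90% power and leave adjustment little to add. Rank tests are also a defensible choice for skewed TG and hsCRP, and the simulations generate log-normal data, which favours a log-scale ANCOVA. All of this stands and limits the size of the point. It does not reverse the ordering: in the second model at 20%, rank ANCOVA also gained about 6 points at ρ 0.4 and 2 at ρ 0.6.

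A log ANCOVA also moves the target from percentage change to a ratio of geometric means. That is true and should be stated openly.

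Four stronger readings are tempting, but the protocol does not support them.

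- **Baseline is thrown away.** This is so only for the level test.
- **The tests are biased by chance imbalance or regression to the mean.** Randomisation makes both act alike on all arms in expectation, and the p-value already allows for chance imbalance.
- **The trial's primary comparison is weakened.** The protocol does not settle that the primary comparison is between arms. Section 6.3 says "For the test of superiority (versus baseline), the ITT population is the primary analysis population", and Section 6.5 says "Hypothesis testing will be undertaken to assess whether this change from baseline in TG levels is significantly different from zero". That conflict is a separate matter.
- **No effect estimate is planned, and randomisation ignores TG.** Estimates and intervals may be left to the SAP. Section 3.5 says only that allocation is "determined according to a non-centre specific randomisation scheme", which is silent on TG.

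**Conclusion.** The point holds as a free improvement in precision. The protocol fixes two unadjusted, unranked between-arm tests although baseline TG is available for every correctly randomised patient. Baseline adjustment is more precise than either test for any slope between 0 and 1.

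Against the percentage-change test, the gain is about 3 to 8 power points at a 15% reduction, allowing for simulation error. At about 20% it is about 0 to 4 points under the main assumptions and up to about 8 with lower correlation and larger SD. Only in that last setting do both planned tests fall below the 90% that Section 6.5 requires while ANCOVA reaches it. SD, correlation and population median are all assumed, and the planned effect depends on reading the two proportions in Section 6.5 as mean reductions. For the secondary variables the direction is the same; the size was not computed.

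**What to change.** - Name one between-arm analysis of TG: ANCOVA of log week-8 TG on arm, with log Visit 2 TG as covariate. Specify Visit 2, because the synopsis places baseline at Visit 2.1, where Table 1 shows no lipid sample.
- Report each dose's adjusted percentage difference from placebo, as a geometric mean ratio, with a 95% CI.
- Pre-specify rank ANCOVA on percentage change as the fallback if residuals are badly non-normal.
- Keep the Mann-Whitney test on percentage change as a sensitivity analysis. Drop the week-8-level test as a deciding test.
- Use the same approach for the secondary variables in Section 6.4.1.2.

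The cost is protocol wording (synopsis, 6.4.1.1 and 6.4.1.2) and matching SAP text. No extra patients, visits or samples are needed.

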6.4.1.2 Lipids and lipoproteins other than Triglycerids

Lipids (other than TGs), apolipoproteins and CRP comprising secondary endpoint (1, 2 and 3) will be analysed in a similar way.

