Initially a Friedman analysis will be performed, then, for comparing basal state against 8 week, inside each group, a Willcoxon test will be performed. For comparing each one of Rosuvastatin groups against placebo group at week 8 a U Man Whitney test will be done. Also, the percentage of reduction –week 8 minus basal- obtained in the placebo group will be contrasted against the percentage of reduction in each one of the Rosuvastatin groups using a U Man Whitney test. In all the cases a p < 0.05 will be considered significant.

Lipids (other than TGs), apolipoproteins and hsCRP comprising secondary endpoint (1, 2 and 3) will be analysed in a similar way.

Adverse events can occur in the dietary lead-in phase and/or the randomised phase of the study. The latter phase will include the period up to 30 days after the last dose of study medication. All adverse events will be classified according to the following:

- Reported during the dietary lead-in period
- Treatment emergent. This is further categorized as:
 - Ongoing from the dietary lead-in period and subsequently worsening during the randomised period, and
 - Starting during the randomized period.

All adverse events will be categorized by the body system and preferred term assigned to the event using National Medical Terminology Officially Accepted terms and listed for each subject. For subjects in the dietary lead-in safety population events occurring during the dietary lead-in phase will be summarised by frequency; in the randomized safety population treatment emergent events will be reported as frequencies in each treatment group. Frequencies of adverse events leading to withdrawal from the randomized period will also be tabulated and reported by treatment group. Adverse events leading to death, serious adverse events and drug related adverse events would be presented similarly.

TABLE OF CONTENTS

PAGE

	TITLE PAGE	1
	PROTOCOL SYNOPSIS	2
	TABLE OF CONTENTS	6
	LIST OF ABBREVIATIONS AND DEFINITION OF TERMS	10
1.	INTRODUCTION	13
1.1	Background	13
1.2	Rationale for this study	14
2.	STUDY OBJECTIVES	14
2.1	Primary objective	14
2.2	Secondary objectives	14
3.	STUDY PLAN AND PROCEDURES	
3.1	Overall study design and flow chart	15
3.2	Rationale and risk/benefit assessment	20
3.2.1	Rationale for study design and control group	
3.2.2	Risk/benefit and ethical assessment	
3.3	Selection of study population	
3.3.1 3.3.2	Study selection record Inclusion criteria	
3.3.3	Exclusion criteria	
3.3.4	Restrictions	

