2.2 Secondary objectives

The secondary efficacy objectives of the study are as follows:

- 1. To evaluate the efficacy of RSV from baseline to week 8 on:
 - a. Non-HDL-C levels
- 2. To evaluate the efficacy of RSV from baseline to week 8 on
 - a. Low-density lipoprotein cholesterol (LDL-C)
 - b. Total cholesterol (TC)
 - c. High-density lipoprotein cholesterol (HDL-C)
 - d. Apolipoprotein A1 (ApoA-1), apolipoprotein B (ApoB) and
 - e. TC/HDL-C, LDL-C/HDL-C, nonHDL-C/HDL-C and ApoB/ApoA-1 indexes.
- 3. To determine the efficacy of RSV in reducing high-sensitive C- reactive protein (hsCRP) from baseline to week 8.

The secondary safety objective of this study is:

• To evaluate the effect of RSV on the incidence and severity of adverse events and laboratory data

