4.2 Secondary variables

Secondary variables are: non-HDL-C; LDL-C; TC; HDL-C; ApoA1; ApoB levels; ApoB/ApoA1; non-HDL-C/HDL-C; LDL-C/HDL-C; TC/HDL-C and hsCRP.

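### Every secondary efficacy test is declared significant at p < 0.05, with no testing order, no condition on the triglyceride result and no supportive label, so the secondary family-wise error is several times 5%

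*Protocol*

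**What the plan says.** Section 4.2 lists eleven secondary variables: "Secondary variables are: non-HDL-C; LDL-C; TC; HDL-C; ApoA1; ApoB levels; ApoB/ApoA1; non-HDL-C/HDL-C; LDL-C/HDL-C; TC/HDL-C and hsCRP". Section 6.4.1.2 says how they are tested: "Lipids (other than TGs), apolipoproteins and CRP comprising secondary endpoint (1, 2 and 3) will be analysed in a similar way".

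The methods referred to are in section 6.4.1.1. They comprise an initial Friedman analysis and two Mann-Whitney comparisons with placebo. The first is on the week-8 value: "for comparing each one of Rosuvastatin groups against placebo group at week 8 a U Man Whitney test will be done". The second is on percentage change, with the placebo result "contrasted against the percentage of reduction in each one of the Rosuvastatin groups using a U Man Whitney test". The section closes with the decision rule: "In all the cases a p < 0.05 will be considered significant". The synopsis repeats all this and adds a within-group test: "for comparing basal state against 8 week, inside each group, a Willcoxon test will be performed".

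Table 5 and section 6.2 define every efficacy variable as percentage change from baseline to week 8. The secondary objectives are numbered 1 to 3, but no testing rule uses the numbering. The hsCRP objective is worded as a claim: "To determine the efficacy of RSV in reducing high-sensitive C- reactive protein (hsCRP) from baseline to week 8". The only statement on multiplicity is in section 6.5, "No adjustment will be applied for the two rosuvastatin groups since the hypothesis testing in each of the treatment groups is independent", and it concerns the TG change from baseline.

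**The concern.** A threshold of 0.05 on each test limits the error of that test only. When any one of many such tests may be called significant, the chance that at least one is falsely significant grows with their number. Here nothing stops a significant hsCRP or ApoA-1 result at one dose from being declared even if TG fails at both doses. Nor is anything said about how many tests were available to produce it.

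The list also contains one quantity twice. TC/HDL-C and non-HDL-C/HDL-C differ by a constant, so one finding could be presented as two that support each other.

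**Working it through.** The protocol states no family-wise error for the secondary variables, so there is no figure of its own to reproduce.

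**Inputs from the protocol.** 11 variables (4.2), two doses each against one shared placebo arm with 1:1:1 allocation (3.5), two Mann-Whitney tests per variable and dose, and p < 0.05 for each (6.4.1.1).

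**Count.**
- Percentage change only: 11 × 2 = 22 tests.
- With the week-8 level tests: 11 × 2 × 2 = 44 tests.
- The Friedman analysis and the synopsis's within-group tests are left out of both counts.

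**Expected false positives if nothing works.** 22 × 0.05 = 1.1, or 44 × 0.05 = 2.2.

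**Reference value under independence.** 1 − 0.95^22 = 0.68. This is too high here, because the variables overlap and the doses share a placebo arm.

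**Allowing for correlation.** The protocol gives no correlations, so these are assumptions:
- between the two dose comparisons, 0.5, which follows from equal arms and a shared placebo;
- between variables, 0.3, 0.5 or 0.8;
- between the level test and the percentage-change test of one variable, 0.5.

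Multivariate normal test statistics were simulated under the null. The table gives the share of simulated trials with at least one statistic beyond 1.96, in either direction or in the favourable direction only. The nominal rate for one test is 0.05 in either direction and 0.025 in the favourable one.

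| Null variables | Tests | Direction | r = 0.3 | r = 0.5 | r = 0.8 |
|---|---|---|---|---|---|
| All 11 | 22 | either | 0.58 | 0.49 | 0.30 |
| All 11 | 22 | favourable | 0.31 | 0.25 | 0.15 |
| All 11 | 44 | either | 0.80 | 0.71 | 0.49 |
| All 11 | 44 | favourable | 0.48 | 0.39 | 0.25 |
| ApoA-1 and hsCRP only | 4 | either | 0.17 | 0.16 | 0.14 |
| ApoA-1 and hsCRP only | 8 | either | 0.29 | 0.28 | 0.24 |

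A second simulation used 100 patients per arm and actual Mann-Whitney tests. It built TC, non-HDL-C and the cholesterol ratios from LDL-C, VLDL-C and HDL-C, so it carries the real overlap. For 22 tests it gave 0.37 to 0.45 in either direction and 0.18 to 0.24 in the favourable direction. For 44 tests it gave 0.60 to 0.67 and 0.34 to 0.39.

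**The duplicated ratio.** Non-HDL-C = TC − HDL-C, so non-HDL-C/HDL-C = TC/HDL-C − 1. Subtracting a constant leaves ranks unchanged, so the week-8 Mann-Whitney tests of the two ratios are identical. For percentage change, let r0 be the baseline non-HDL-C/HDL-C and d its change. The two percentage changes are d/r0 and d/(r0 + 1). They always have the same sign, and their quotient is r0/(r0 + 1). For an assumed r0 of 4 to 6 this lies between 0.80 and 0.86, so the two rankings, and hence the tests, are nearly the same but not identical.

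**The case against.** The strongest objection is that a global null contradicts the protocol. Section 1.2 cites LDL-C falls of 45 to 50% and HDL-C rises of 7 to 10%, and TC, non-HDL-C and the cholesterol ratios are built from these components. A false positive needs a true null. This stands: the all-null rows are a ceiling, and HDL-C is a poor example of an unaffected variable. But the protocol cites no expected effect for ApoA-1 or hsCRP, and with those two alone the either-direction error is still about three to six times 5%. Counting only favourable results on the 4 percentage-change tests, it is 0.07 to 0.09 against 0.025.

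A reader might infer that a false secondary efficacy claim is more likely than not. The documents do not support that. Over the assumed correlations, 22 tests pass 0.50 only at the low end, and only if a significant worsening counts as a claim. With favourable results alone, neither count reaches 0.50. The week-8 level test is also a second analysis of an endpoint that Table 5 defines as percentage change, so 22 is the fairer count.

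It can also be said that this is a phase IV study with one primary variable, that most secondary objectives are worded as evaluation, and that alpha allocation commonly belongs in the SAP, which section 6.1 promises and which is not shown. Silence here would be no finding. The protocol is not silent, though: it fixes the threshold for all cases and carries the method over to the secondaries. That the threshold travels with the method is a reading of 6.4.1.2, but the natural one.

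Finally, listing both ratios is ordinary lipid reporting, and the protocol does not call them independent support. That is fair, and it limits the point to how they are counted.

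**Conclusion.** The concern holds as a matter of structure. The protocol lets any of 22 tests, or 44 with the level tests, be declared significant at 0.05 whatever happens to TG, so the secondary family-wise error is uncontrolled and several times 5%.

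Its size depends on assumed correlations and on which variables are truly unaffected. For 22 tests under a global null it is about 0.30 to 0.58 two-sided and 0.15 to 0.31 in the favourable direction. In the more realistic case of two unaffected variables it is 0.14 to 0.17 for 4 tests and 0.24 to 0.29 for 8, two-sided. The count, the missing order and gate, and the ratio identity need no assumption. The point concerns what may be concluded from the secondaries; it does not touch the TG analysis or the sample size.

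**What to change.** Amend section 6.4.1.2, and the matching synopsis text, before unblinding:

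1. Use one test per secondary variable: percentage change against placebo, as in Table 5. Report week-8 levels descriptively.
2. For each dose, declare non-HDL-C (secondary objective 1) significant only if the TG percentage-change comparison for that dose is significant at the level the protocol uses for TG.
3. Report objectives 2 and 3 as supportive, with estimates, 95% confidence intervals and nominal p-values.
4. Limit the statement that p < 0.05 counts as significant to TG and non-HDL-C.
5. State that TC/HDL-C and non-HDL-C/HDL-C carry the same information and will not be counted as separate supporting results.

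This needs no alpha-passing scheme, which the protocol does not have. Each dose's two-step sequence stays at 5%. Across both doses the bound is 2 × 0.05 = 0.10, because the protocol's choice not to adjust for two doses is left as it is.

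The cost is wording only, with no extra patients or data. The downside is that effects on LDL-C, TC, HDL-C, the apolipoproteins, the ratios and hsCRP are reported as supportive rather than confirmed.
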